#### Details of Ph2 extended short term trials:

Ph2a Part 1-n=17 (March 2008), the fruit component alone of the bars was tested for efficacy: none.

**Ph2a-Part 2**- n= 12 (April 2008), the fruit plus soluble fiber componets alone were tested for efficacy: none.

**Ph2a-Part 3**- n=11 (June 2008) -the full bar formulation with adjusted B vitamins as noted above following the Ph 2 finding of homocysteine elevation was tested with significant HDL elevation and Hcy reduction.

**Ph2a-Part 4**- n=26 (September 2008)- two alternate forms of soluble fiber (beta glucan vs inulin) were tested in a randomized study design that confirmed efficacy (HDL elevation and Hcy reduction) of the original formulation (with beta glucan) studied in Part 3.

**Ph2a-Part 5**- n= 16 (April through June 2009)- A longer - 2 month- trial of yet another form of soluble fiber (HPMC) gave new and favorable outcomes for insulin sensitivity but blunted the HDL and Hcy effects due to hypothesized excess barrier function of this highly viscous fiber.

**Ph2a-Part 6**- n=8 (September 2008)- A repeat trial of the original formulation tested in Part 3 (and one arm of Part 4) confirmed the reliability and reproducibility of the favorable HDL and Hcy effects.

**Ph2a-Part7**- n=23, with 3 dropouts due to palatability concerns (for the first time, Mar-May, 2010)- a 2 mo trial of the original formulation (used in parts 3, one arm of 4 and 6) plus the addition of a new form of Vitamin K. The principal outcomes of HDL elevation and Hcy reduction were confirmed but new palatability questions were raised that made us question the feasibility of testing of our current formulation in a high risk population from the Healthy Hearts clinic.

**Ph2a-Part 8**- n=10 (Feb 2010- note run out of sequence - ie just before part 7 due to the timing of bar production with the USDA- these bars were ready first- fewer required as this was a short- 2wk- and smaller trial)- this was a deconstruction trial designed to test the synergistic requirement of fruit and soluble fiber in the bars. Whereas the fruit and fiber have no effect alone (Ph2a-Part 2), bars studied in this small trial without fruit or beta-glucan soluble fiber did not have the anticipated effect on HDL or Hcy.

**Ph2a-Part 9-** n= 9 (Dec 2010)- This was a newly formulated bar that incorporates all of the key ingredients of our past successful trials and adds two new components felt to be important for optimal metabolism, lactate and a resistant starch, and importantly adds freeze-fried blueberry, a new form of fruit additive with unanimous participant agreement vis-à-vis the favorable impact on texture and palatability. We were encouraged to see improvements in insulin sensitivity and LDL-cholesterol in several participants in this trial- a finding we have not seen since Ph2a-Part 5 that tested HPMC- but interestingly we saw comparable blunting of our HDL and Hcy efficacy. This prompted the hypothesis that the addition of freeze-dried blueberry with its high pectin viscous, soluble fiber content, might have, like HPMC, provided both benefit and excessive barrier function. We are currently enrolling a repeat trial with this same bar in adult participants who have been in previous trials with half as much freeze dried blueberry to test this hypothesis.

It is of note that the main outcome of the bar, a significant increase in HDL, was only mildly attenuated in Ph2a-Part 9 (a comparable 5% increase in HDL was observed but at a borderline p value of 0.05, but there was still a favorable trend towards the large and buoyant HDL subspecies. Again, it is provocative

that in this same trial, several participants experienced improved insulin sensitivity and LDL reduction. These findings did not reach significance in the small, relatively insulin sensitive and normolipidemic cohort of 7 healthy adults but would be very positive added benefits to this nutrient intervention if replicated in the proposed high risk population.

Ph2a Part 10 We are currently reevaluating this near final formulation from Ph2a Part 9, a repeat of Part 9 with less freeze-dried blueberry.

The majority of participants in all trials have reported a significant satiating effect of the CB. When feedback from all three adult pilot trials of the current bar formulation are pooled, the mean drop in the hunger score on a 1 to 10 analog scale is 4.0 + /- 1.8 units 20 minutes after ingestion. None of these preliminary adult trials have been accompanied by weight loss, but neither have weight loss or specific nutrition and activity lifestyle guidelines been offered. The only instruction has been to eat a bar twice daily, with water. Many participants comment that the bars serve as a meal replacement. Therefore, despite the 200 kcal delivered with bid intake, there has been sufficient dietary adjustment to avoid any significant increase in weight after either the 2 week or 1 month trials. We have observed a suggestion of favorable weight redistribution: WC drops from a mean of 87.3 + /- 12.6 to 86.0 + /- 11.2 cm, p = 0.07.

Taste testing of the former formulation (deemed less palatable than the latest formulation we propose now to study) among 15 obese (BMI 47.8 +/- 19.5) preadolescents and teens (age 12.9 +/- 3.4) in the HH clinic was conducted in the summer of 2010 with the sweet/sour flavored bars. On an analog scale from 1 to 10, where 1 was unfavorable, 5 was acceptable, and 10 was favorable, the mean score was 5.9 +/- 3.1, (median 6). 67%, 73%, and 87% of participants could appreciate the fiber, fruit, and chocolate respectively. All but one said they would eat the bars if they knew they were good for them, including the 6 who scored the bar below 5 for taste. The single participant, who said he would rather not eat them if they were healthy, actually liked the bars, assigning a taste score of 8. We are encouraged by this generally positive reception to the nutrient-dense CB that our plan of studying an even more palatable version in a pediatric cohort who present to HH for weight management will be feasible. We are not sure however, that twice daily intake will be sustainable for adolescents beyond the first 2 wk or the study, as we have not yet tested the bar in a pediatric population. Therefore the study design of weekly group visits to closely monitor adherence for the 2 mo trial and the incorporation of parent/quardian participants for daily reinforcement was chosen.

11. Study Design: (Check all that apply).					
☐ Placebo ☐ Blinded ☐ Randomized ☐ Investigational intervention without random assignment					
If this study	If this study has any of the formal designations below, please indicate below:				
☐ Phase I	□ Phase II	☐ Phase III	☐ Phase IV	☐ Open Label Extension	
Additional description of general study design. Sequentially list all procedures, drugs or devices to be used on human subjects. Describe any use of placebos and indicate whether subjects will be randomized in this study. Attach flow diagram if appropriate. If there are any investigational drugs, devices or biologic agents used in this study, please complete and attach the FDA Form 1572. If this is an investigator-initiated study, attach the FDA Investigational Drug Application.					

# **Study Population**

**12. Characteristics of the Subject Population:** Describe the gender, ethnic background and health status. Provide a candid discussion of potential problems, if any, related to the study population. Explain the rationale for the use of special classes such as pregnant women, children, prisoners, wards of the court, or other vulnerable populations. If women, minorities, non-English speaking subjects or children are excluded, provide written justification.

Children and their parent/guardian will be recruited from the Oakland branch of the Children's Hospital Healthy Hearts (HH) preventive cardiology clinic.

The HH Clinic in Oakland sees an average of 12 new referrals per week, interspersed with follow-up visits over 2 ½ clinic days, serving a high proportion of disadvantaged inner city families of color; 24% African American, 58% Hispanic (predominantly Mexican or Latin-American), 6% Asian/Pacific Islander, 12% White. All of the children referred for weight management have a BMI > 85th percentile for age and gender (92% > 95th percentile).

Target enrollment will be 32 boys and girls and one parent guardian. The 32 boys and girls will be at > 95th percentile BMI who do not meet exclusion criteria. Families consent at the time of their HH intake visit to inclusion in the HH data base and opt in and out of the possibility of contact for future research. Only families who have not opted out of this provision will be contacted.

We have had good adherence and follow-up in both HH clinic and with lifestyle counseling groups recruited from the HH clinic population, so are optimistic we will be able to identify families who are able to sustain this level of commitment. The plan to run the groups in the late afternoon or weekends should help minimize interference with adult work and child school schedules..

Because we have seen improvement in metabolic parameters with the CBs in persons along a wide spectrum of weight and presenting metabolic states, and because the 8 week group counseling sessions expand upon what is possible in one-on-one clinical visits, we do not feel that prior visits in the HH program preclude participation. On the contrary, prior visits as well as continued involvement in the HH clinical program after completion of the proposed study are deemed critical to reinforcement of lifestyle principles and long term success with weight management. Similarly there is no contraindication to parental participation if the parent is of normal weight. Most of the metabolic benefits documented to date in CB trials have been in healthy, normal weight adults.

**13.** Inclusion/Exclusion Criteria: Indicate the criteria for exclusion and inclusion and explain the system for equitable selection of subjects.

#### INCLUSION: Child:

- referral to HH clinic for weight management,
- age 14-18 yr,
- BMI > 95th percentile, and
- willingness to eat the CB bid after tasting a sample,
- Speaks English (as group sessions will be run in English),
- willingness to attend 8 weekly group counseling sessions.

#### INCLUSION: Parent/guardian:

- willingness to attend the 8 weekly sessions with their child.
- willingness to eat a CB

•	report at the w	eekly visits
---	-----------------	--------------

EXCLUSION: Child and parent/guardian:

- diabetes mellitus (49);
- hypertension (>95th percentile systolic or diastolic pressure);
- glucocorticoid therapy (> 15 mg/m2/d) (50) or
- inhaled steroid therapy for asthma (>1.5 mg/d or >0.75 mg/d for fluticasone propionate), (51) since adrenal suppression can occur that will affect inflammation and insulin sensitivity;
- weight loss drugs;
- lipid, or blood pressure lowering medication.

# ADDITIONAL EXCLUSION: Parent/guardian:

• moderate or severe untreated hypertension but a parent can be on blood pressure lowering medication, if they have been on the dose stably for more than 3 mo preceding the study.

# **14. Eligibility for Study:** How is eligibility determined and by whom?

[name], study coordinator (to be named), [name], and HH physicians Drs. [name] and [name], will determine eligibility on the basis of review of the HH intake clinic record. All follow-up questioning by phone contact will be conducted by the research team, Drs. [name], [name], and the study coordinator (to be named).

# 15. Duration of Subjects' Participation in the Study (include follow-up if applicable):

Once potential parent guardian/child dyads are identified in the HH data base, they will be contacted and if interested, scheduled for a visit in the PCRC for consent and screening. The goal is to identify 32 eligible dyads over one month. Interested families will have an opportunity to taste the bars at the time of informed consent. When all baseline assessments are completed the dyads will begin the 8 wk group therapy, receive weekly distribution of each successive week's supply of CBs and scheduled follow up visits. It is anticipated that a total of 4 months is required to complete the study.

# 16. Planned Enrollment at CHRCO: Number of subjects needed to complete the study. 17. Enrollment plan: If you expect failed screenings or subject withdrawals, will they be replaced until the appropriate numbers of subjects have completed the study? If No, explain below. 18. Planned Enrollment at CHRCO: Number of subjects needed to complete the study. 26. 64 (32 adolescents & 32 adults) 27. Enrollment plan: If you expect failed screenings or subject withdrawals, will they be replaced until the appropriate numbers of subjects have completed the study? If No, explain below. 28. Very No □ N/A

We will make every effort to identify at the time of enrollment parent/child dyads who can commit to good study adherence and its completion. Given the 8 weekly group sessions that are built into this intervention, it would not be tenable to enroll additional children once the groups are underway. We are powered to see significant results in our main outcome, HDL cholesterol, with 12 per group so can accommodate up to 15% attrition in the control group (of 14 dyads) and 33% attrition in the intervention group (of 18 dyads). Opting for a slightly larger intervention group will both insure the adequacy of both adolescent and adult numbers for significance and may also increase the information available from our exploratory assays.

**18. Recruitment:** What methods will be used to identify and recruit potential subjects? Attach a copy of all planned advertisements, flyers and letters, etc. to potential subjects.

We will identify potential recruits within our HH research data base. The families in this data base have consented to be contacted for potential research studies. Interested families will be invited to attend an information session where they will learn about the study, have any questions answered and have an opportunity to taste the bars. If they are still interested in participating, the consent will be signed at this session and a baseline assessment will be scheduled on the PCRC.

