#### **Risk and Benefit Assessment**

**22. Potential Risks and Discomforts:** Describe any potential risks or likely adverse effects of the drugs, biologics, devices or procedures subjects may encounter in the study. State the potential risks – physical, psychological, social, legal or other – connected with the proposed procedures and assess their likelihood and seriousness.

There is a small risk of pain, bruising, or infection with venipuncture. There are possible psychological risks of completing questionnaires, particularly those aimed at identifying the participant's eating and activity habits. The acquisition of physical measures, especially weight and abdominal circumference, may make some participants uncomfortable. Participation in research may involve a loss of privacy, but all health information will be handled as confidentially as possible with substitution of study ID numbers in place of names on all study forms, questionnaires, and blood tubes.

23. Safety Precautions for Minimizing Risks: Describe the procedures for minimizing any potential risks. Where appropriate, discuss provisions for ensuring necessary medical or professional intervention in the event of adverse effects to the subject.

The small risk of venipuncture will be minimized by using trained phlebotomists or experienced MD's and strict sterile technique. The acquisition of all physical measures will be done with care to protect privacy. Participation in research may still involve some loss of privacy, but all health information will be handled as confidentially as possible with substitution of study ID numbers in place of names on all study forms, questionnaires, and blood tubes.

24. Benefit Ratio: What is the risk benefit ratio of this research, compared with available alternatives? Describe the potential benefits the subjects may receive as a result of their participation in the research and what benefits to society may be expected. For greater than minimal risk research involving children there must be the prospect of direct benefit to the individual subjects.

Note: The potential benefits of the research must justify the risks to human subjects. The risk benefit ratio of the research must be at least as favorable for the subjects as that presented by standard treatments for their condition. When comparing the risk/benefit ratio of research with that of available alternatives, the alternative of doing nothing should be included in the analysis.

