#### **Informed Consent**

29. Capacity to Consent: Will all subjects have the capacity to give informed consent? If not, describe the likely range of impairment and explain how, and by whom, their capacity to consent will be determined.

Adult participants will have full capacity to consent for themselves and for their adolescent children. Adolescent participants will have capacity to assent.

30. Study Personnel Administering the Consent Process: Please identify by name and training the individual(s) who will be authorized to describe the research to subjects or their representatives, and to invite their participation. To insure that subjects give complete informed consent and are able to ask and have answered all questions regarding the nature of their participation, the personnel administering the consent must have appropriate training and background.

Drs. [name], the study coordinator (to be named), [name] will take responsibility for obtaining the study consents and assents.

31.		ocess of Consent: Please discuss how the consent process will be conducted lowing elements:	ed, describing the
	a)	The environment and location where the informed consent will be solicited;	
	b)	Opportunities for the potential subjects to discuss their participation with family signing the consent form;	y or others before
	c)	How and by whom it will be determined whether the subject or their I representatives understand the information provided; and	egally authorized
	d)	The types of forms used (e.g., adult consent form, parental permission form translations to other languages, etc.)	n, combined form,
b) be	The rev	althy Hearts (HH) clinic and/or the PCRC will be the sites for consent study requirements, risks, and benefits, and the complete voluntary nature of piewed	•
info	orm	[name], [name], and the study coordinator to be named ed consent and confirm study requirments are understood. It consents and child assents	) will obtain the
32.	As	sent of Minor: For subjects age 7 through 17:	er 7 or adult)
	a)	Considering the subject's potential capacity and medical condition, what is the suggested age of the minors to provide assent?	14-17
	b)	Detail below whether the assent should be in writing (a separate assent fo child), and/or obtained orally.	rm signed by the
Th	ie se	eparate assent will be in writing for signature by the child.	

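### As item 18 is written, families taste the study bar before consent is signed; assent is not timed against the tasting, and the visible protocol describes no ingredient-allergy check and no risk from eating the bar

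*Protocol*

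**What the plan says.** Several items of the protocol bear on the first contact with the bar.

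- **Item 18, Recruitment.** Families are invited to an information session "where they will learn about the study, have any questions answered", and they "have an opportunity to taste the bars. If they are still interested in participating, the consent will be signed at this session". The baseline assessment is scheduled afterwards.
- **Item 15, Duration of participation.** Interested dyads are "scheduled for a visit in the PCRC for consent and screening", and "Interested families will have an opportunity to taste the bars at the time of informed consent".
- **Item 13, child inclusion criteria (age 14-18).** One criterion is "willingness to eat the CB bid after tasting a sample". The parent criterion asks for willingness to eat a bar and sets no tasting condition.
- **Item 14, Eligibility.** The team and clinic physicians "will determine eligibility on the basis of review of the HH intake clinic record", with follow-up questions by phone.
- **Item 32, Assent.** The "assent will be in writing for signature by the child"; the suggested ages are 14-17.
- **Item 22, Risks.** It opens with "There is a small risk of pain, bruising, or infection with venipuncture" and goes on to questionnaires, physical measures and privacy.

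**The concern.** A step that decides eligibility is a study procedure, and here it involves swallowing a research product. Permission for such a step should be in place before it happens, especially for minors. The only earlier permission that the protocol describes is agreement to be contacted about research, which does not extend to eating the product.

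The product has many ingredients. Item 10 lists a fruit base, protein, glutamine, omega-3 fatty acids, mixed fibers, thirteen vitamins, choline and nine minerals, with ground coffee beans in one of the two flavors. Tasters of a former version noticed chocolate. The near-final formulation was still being re-evaluated. A reaction on first ingestion is a foreseeable hazard of any such food, and the visible eligibility and risk items are silent on it. At stake are participant protection and the validity of consent for that step. No treatment estimate is affected.

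**Working it through.** The point concerns the order and content of procedures. The only arithmetic is a count, so the check sets the items side by side.

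1. **Order under item 18.** The sequence is explanation and questions, tasting, then signature. Signature is conditional on interest remaining after the tasting, so the tasting feeds the decision to sign and comes before it.

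2. **Order under item 15.** Tasting coincides with consent. That is compatible with signature first or tasting first. Items 15 and 18 therefore do not give opposite instructions: one states an order and the other leaves it open.

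3. **Place.** Item 15 has a PCRC visit for consent and screening. Item 31 names the Healthy Hearts clinic and/or the PCRC as consent sites. Item 18 does not say where the information session is held. No conflict of place is established.

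4. **Assent.** Item 32 says that assent is written and separate. Neither item 31 nor item 32 places it before or after the tasting.

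5. **Who must taste.** The tasting condition is in the child criteria only. Planned enrollment is 64 people, 32 adolescents and 32 adults. Every enrolled adolescent must have tasted to satisfy the criterion, so the firm minimum is 32. Parents are offered a taste and need not take it. Of the 32 adolescents, 18 are to be assigned to the bar and 32 - 18 = 14 to control. For those 14 the screening sample is the only planned exposure to the bar, and under item 18 it falls before signature.

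6. **Allergy check.** The exclusions in item 13 cover diabetes, hypertension, steroid therapy, weight-loss drugs, and lipid or blood-pressure medication. None concerns food allergy or intolerance. Item 14 describes record review and phone questions, but does not say that they cover allergy, that they are complete before the tasting, or that the child's clinic record holds the parent's history. The visible text describes no check at any stage, so the gap runs through the whole trial and is not confined to the tasting.

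7. **Disclosed risks.** Items 22 and 23 cover venipuncture, questionnaires, physical measures and privacy. Neither mentions eating the bar.

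**The case against.** The strongest reply is that families are not exposed blind. Item 18 puts explanation and questions ahead of the tasting, and consent follows at the same session. Clinic records are reviewed and phone questions asked. What is offered is an opportunity to try a sample, which need not be a whole bar. Earlier experience is also reassuring as far as it goes: item 10 reports 15 obese preadolescents and teens from the same clinic tasting a former version with no reaction mentioned, no gastroenterological symptoms in nine adults over two weeks, and microbiological testing of the bars. Ingredient or allergy wording would naturally sit in the consent and assent forms, which were removed before review.

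Most of this stands as a limit on the point. A reader might infer that the first exposure escapes every safeguard; the information step, record review and phone contact show that this is too strong. A reader might also count everyone who attends as exposed, but tasting is optional for parents and the protocol gives no attendance figure. Nor does the protocol support an argument about drop-out confined to the bar arm: it gives no reaction rate, and a reaction at the tasting would appear before randomization, which item 19 places after the baseline bloodwork.

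What the reply does not remove is the order in item 18. Whatever the forms say, a form signed after the tasting cannot authorize that tasting. Small tolerability experience in adults, and one tasting of a former version, do not exclude allergy to an ingredient.

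**Conclusion.** The point holds in a limited form. Item 18 places a screening procedure, ingestion of the study bar, before signed consent. Item 15 does not settle the order, and item 32 does not time the assent. At least 32 adolescents are affected; any larger number needs an attendance assumption that the documents do not support. Separately, the visible eligibility and risk items contain no ingredient-allergy check and no ingestion risk at any stage.

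This rests on a plain reading of the sequence in item 18 and on the text as shown. The removed consent pages may contain allergy or ingredient wording. The protein source and allergen content are not stated and no reaction rate is given, so the size of the risk cannot be assessed. Power and the planned comparisons are unaffected. It should be corrected before recruitment because the change is cheap and bears on participant safety.

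**What to change.** - Align items 15, 18, 31 and 32 on one sequence: information and questions, signed consent and written assent, tasting, then scoring of the child tasting criterion.
- Before the tasting, show the ingredient list, ask both members of the dyad about allergy or intolerance to the listed ingredients, and reflect this in the shared criteria of item 13.
- Address reactions to eating the bar in items 22 and 23, and keep the consent and assent forms consistent with them.

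Reordering the signature alone would not be enough, since the missing allergy check is a separate gap. The cost is protocol and form wording, plus a few families who sign and then fail screening at the tasting. No extra visit, staff or change in sample size is needed.
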